6.4.1.2 AE Overview

An AE overview without SOC and PT presents the number and percentage of subjects with any of the following AEs: any AE; mild AE; moderate AE; severe AE; moderate or severe AE; AE related to study drug; SAE; SAE related to study drug; AE leading to study drug discontinuation; hepatic-related AE; potential drug abuse AE; cardiovascular AE; suicidality AE; and local irritation AE.

An AE overview is produced for each analysis period (pre-treatment, on-treatment) for the safety analysis set.

6.4.1.3 Pre-treatment AEs by SOC and PT

Pre-treatment AEs are tabulated by SOC and PT for the safety analysis set for the following endpoints:

- AEs by intensity (total, mild, moderate, severe, moderate or severe, not reported)
- SAEs.

AEs are displayed in descending order of overall frequency within SOC and PT.

6.4.1.4 On-treatment AEs by SOC and PT

On-treatment AEs are tabulated by SOC and PT for the safety analysis set for the following endpoints:

- AEs by intensity
- TEAEs by intensity
- AEs associated with study drug by intensity
- AEs by relationship to study drug (related, possibly related, unlikely related, not related, not reported)
- SAEs
- AEs leading to study drug discontinuation
- Hepatic-related AEs by intensity *
- Cardiovascular AEs *
- Suicidality AEs *
- Local irritation AEs by intensity *.

AEs of special interest are asterisked (“*”). AEs are displayed in descending order of zavegepant frequency within SOC and PT.

6.4.2 Laboratory Tests

Laboratory tests are analyzed using results from the external central laboratory CCI [REDACTED] which identifies expired kits, and from local laboratory tests reported on CRFs. The central laboratory reports both laboratory collection date and time, whereas CRFs capture only laboratory collection date.

Clinically significant laboratory abnormalities are identified as grade 3 to 4 laboratory test results. Refer to the Zavegepant Core SAP for laboratory tests of clinical interest for analyses, including identification of those with toxicity grades.

The following by-subject laboratory test listings are provided for the enrolled analysis set:

- Select laboratory test groups: hematology (both SI and US units)*; serum chemistry (both SI and US units)*; urinalysis (US units only)*; pregnancy (US units only)*; endocrinology, serology, drug screen, and miscellaneous laboratory tests (US units only). The pregnancy listing identifies positive pregnancy tests, which are defined as serum or urine pregnancy tests with either (a) “positive” character value, or (b) numeric value ≥ 25 U/L.
- Liver function test (LFT) values and ratios to ULN (i.e., alanine aminotransferase [ALT], aspartate aminotransferase [AST], total bilirubin [TBL], and alkaline phosphatase [ALP]) for both US and SI units*. The listing displays all LFT results over time for subjects with select LFT elevations (ALT or AST $> 3x$ ULN; ALP or TBL $> 2x$ ULN) at any time point.

- Creatine kinase (CK) elevation questionnaire.

Listings display toxicity grades and identify expired kits from the central laboratory, if applicable, and those marked with “*” display COVID-19 visit impact code for visits impacted by COVID-19 (see Section 9.1.5.2). Refer to the Zavegepant Core SAP for listing contents.

6.4.2.1 *Laboratory Test Abnormalities*

On-treatment laboratory test abnormalities are tabulated as the number and percentage of subjects in the safety analysis set in the following frequency tables:

- Worst (highest) on-treatment laboratory test abnormality for each graded laboratory test.
- Laboratory test toxicity grade shift from baseline to the worst on-treatment toxicity grade for each graded laboratory test.
- Laboratory test low/normal/high shifts from baseline to any abnormal on-treatment value for each laboratory test with normal ranges.

Refer to the Zavegepant Core SAP for toxicity grade categories and additional details.

6.4.2.2 *Liver Function Test Elevations*

Refer to the Zavegepant Core SAP for additional details.

LFT Elevations: Cumulative, Mutually Exclusive, and Composite

The number and percentage of subjects with LFT elevations are tabulated separately for each analysis period (pre-treatment, on-treatment) for the safety analysis set. LFT elevations are based on fold changes above ULN.

LFT ULN Shifts from Baseline to Worst Elevation

LFT ULN shifts from baseline to the worst (highest) on-treatment LFT elevation are tabulated as the number and percentage of subjects in the safety analysis set in pre-specified elevation categories.

eDISH Scatter Plot

An evaluation of drug-induced serious hepatotoxicity (eDISH) scatter plot displays the maximum TBL ratio of value to ULN on the y-axis versus the maximum ALT ratio of value to ULN on the x-axis by treatment group, where both maxima are on treatment but not necessarily concurrent.

6.4.2.3 *Laboratory Test Changes from Baseline*

Values and changes from baseline in laboratory tests are tabulated as continuous variables at baseline and the end of treatment visit.

If a subject has multiple values in the end of treatment analysis visit window, then a single value is selected using the following hierarchy as available:

- Non-missing viable value collected last. If there are multiple viable values on the same date, then the following hierarchy is used as available:
 - Last central laboratory test value collected timewise with the last accession identifier.
 - Last local laboratory test value entered.

Viable laboratory test values are defined as those from (1) kits from the central laboratory that are not expired (see Section 6.4.2), or (2) local laboratory tests reported on CRFs.

- Non-missing value from an expired kit from the central laboratory collected last. If there are multiple values on the same date, then the value with the last accession identifier is used.

6.4.3 Vital Signs and Physical Measurements

All parameters are reported with measurement date only (no time).

Vital signs include systolic blood pressure, diastolic blood pressure, heart rate, temperature, and respiratory rate.

Physical measurements include height (collected at screening only), weight, and BMI.

A by-subject listing of vital signs and physical measurements is provided for the enrolled analysis set, and displays COVID-19 visit impact code for visits impacted by COVID-19 (see Section 9.1.5.2).

6.4.3.1 Vital Sign and Physical Measurement Changes from Baseline

Values and changes from baseline in vital sign and physical measurement parameters are tabulated as continuous variables at baseline and the end of treatment visit.

If there are multiple values on the same measurement date, then the last value entered is used.

6.4.3.2 Vital Sign and Physical Measurement Abnormalities

On-treatment vital sign and physical measurement abnormalities are tabulated as the number and percentage of subjects in categories specified in the Zavegepant Core SAP.

6.4.4 Electrocardiogram

ECG parameters include RR, QRS, PR, QT, QTcF, and ventricular heart rate, which are measured with both date and time by the external source CCI

A by-subject listing of ECG results is provided for the enrolled analysis set, and displays COVID-19 visit impact code for visits impacted by COVID-19 (see Section 9.1.5.2).

6.4.4.1 *ECG Changes from Baseline*

Values and changes from baseline in ECG parameters are tabulated as continuous variables at baseline and the end of treatment visit.

If there are multiple values on the same measurement date and time, then the value with the last ECG reference identifier is used.

6.4.4.2 *ECG Interpretation Shifts from Baseline to Worst Category*

ECG interpretation shifts from baseline to the worst on-treatment category are tabulated as the number and percentage of subjects with normal, abnormal, and clinically significant abnormal interpretations.

6.4.4.3 *ECG Abnormalities*

On-treatment ECG abnormalities are tabulated as the number and percentage of subjects in the categories specified in the Zavegepant Core SAP.

6.4.5 **S-STS**

The S-STS is a prospective rating scale that contains 16 patient-reported questions and 6 clinician-reported questions to track both treatment-emergent suicidal ideation and behaviors. Refer to the Zavegepant Core SAP for calculation of the S-STS ideation subscale, behavior subscale, and total scores.

Values and changes from baseline in the self-reported S-STS ideation subscale, behavior subscale, and total score are tabulated as continuous variables at baseline and the end of treatment visit. The number and percentage of subjects in each change from baseline category (i.e., < -1, -1, no change, 1, > 1) are also presented for the ideation subscale, behavior subscale, and total score.

A by-subject listing of S-STS is provided for the enrolled analysis set, and displays COVID-19 visit impact code for visits impacted by COVID-19 (see Section 9.1.5.2).

Refer to the Zavegepant Core SAP for the listing contents.

6.4.6 **Safety Narratives**

A by-subject listing of safety narrative subject identifiers is provided for the following select events and analysis sets as columns:

- All deaths for the enrolled analysis set
- On-treatment SAEs for the safety analysis set treated with zavegepant
- All AEs leading to discontinuation of study drug for the safety analysis set treated with zavegepant

- On-treatment events of special interest for the safety analysis set treated with zavegepant:
 - ALT or AST > 3x ULN
 - ALT or AST > 3x ULN concurrent with TBL > 2x ULN
 - TBL > 2x ULN
 - ALP > 2x ULN
 - Select hepatic-related AEs, i.e., PTs containing cirrhosis, hepatic failure, hepatitis, jaundice, or liver failure
 - Cardiovascular AEs
 - Suicidality AEs.

Refer to the Zavegepant Core SAP for additional details.

6.5 Outcomes Research

Outcomes research endpoints are exploratory, and are assessed by as-randomized treatment group at 24 hours postdose using the eDiary for the efficacy analysis set. Postdose data are slotted into the 24-hour postdose analysis window automatically by the eDiary (see Section 7.5.3).

Analyses are based on observed data without imputation and regardless of rescue medication use.

Refer to the Zavegepant Core SAP for details about outcomes research rating scale and questionnaires.

6.5.1 MQoL

Impact of treatment on patient-reported quality of life is assessed using the MQoL Version 3.0, which is a 15-item questionnaire that has been validated in migraine patients to measure the short-term impact of treatment within 24 hours. The MQoL consists of 15 items across the following 5 domains: (1) work functioning; (2) social functioning; (3) energy/vitality; (4) migraine symptoms; (5) feelings/concerns. Refer to the Zavegepant Core SAP for the calculation of the total and domain scores and their respective categories.

MQoL total, domain, and item scores are tabulated by as-randomized treatment group as (1) continuous variables, and (2) the number and percentage of subjects in the categories defined in the Zavegepant Core SAP.

A by-subject listing of MQoL is provided for the enrolled analysis set, and presents the total score, domain scores, and item scores for each domain.

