3.1.2 Secondary Objectives

1. To compare zavegepant with placebo for pain relief at 2 hours postdose.
2. To compare zavegepant with placebo for return to normal function at 2 hours postdose according to the Functional Disability scale.
3. To compare zavegepant with placebo for sustained pain relief from 2 to 24 hours postdose.
4. To compare zavegepant with placebo for sustained pain relief from 2 to 48 hours postdose.
5. To compare zavegepant with placebo for sustained pain freedom from 2 to 24 hours postdose.
6. To compare zavegepant with placebo for sustained pain freedom from 2 to 48 hours postdose.
7. To compare zavegepant with placebo for phonophobia freedom at 2 hours postdose.
8. To compare zavegepant with placebo for photophobia freedom at 2 hours postdose.
9. To compare zavegepant with placebo for pain relief at 60 minutes postdose.
10. To compare zavegepant with placebo for return to normal function at 60 minutes postdose according to the Functional Disability scale.
11. To compare zavegepant with placebo for pain relief at 30 minutes postdose.
12. To compare the zavegepant with placebo for return to normal function at 30 minutes postdose according to the Functional Disability scale.
13. To compare zavegepant with placebo for pain relief at 15 minutes postdose.
14. To compare zavegepant with placebo for return to normal function at 15 minutes postdose according to the Functional Disability scale.
15. To compare zavegepant with placebo for rescue medication use within 24 hours postdose.
16. To compare zavegepant with placebo for nausea freedom at 2 hours postdose.
17. To compare zavegepant with placebo for pain relapse from 2 to 48 hours postdose.

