3.1.3 Exploratory Objectives

1. To evaluate zavegepant relative to placebo for pain freedom at all scheduled time points postdose.
2. To evaluate zavegepant relative to placebo for pain relief at all scheduled time points postdose.
3. To evaluate zavegepant relative to placebo for freedom from MBS at all scheduled time points postdose.
4. To evaluate zavegepant relative to placebo for return to normal function at all scheduled time points postdose.
5. To evaluate zavegepant relative to placebo for phonophobia freedom at all scheduled time points postdose.
6. To evaluate zavegepant relative to placebo for photophobia freedom at all scheduled time points postdose.
7. To evaluate zavegepant relative to placebo for nausea freedom at all scheduled time points postdose.
8. To evaluate zavegepant relative to placebo for the Migraine Quality of Life Questionnaire (MQoL).
9. To evaluate zavegepant relative to placebo for the Preference of Medication (PoM).
10. To evaluate the safety and tolerability of zavegepant in the acute treatment of migraine, as measured by the frequency of adverse events of moderate or severe intensity, serious adverse events, clinically relevant laboratory test abnormalities, and nasal inspection abnormalities.
11. To evaluate zavegepant relative to placebo for the Sheehan-Suicidality Tracking Scale (S-STS).

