Intercurrent Events	Rescue medication use at or before time point: Composite strategy, i.e., intercurrent event captured in endpoint definition
Objective	Phonophobia freedom at all time points postdose
Efficacy Endpoint	At each time point postdose, percentage of subjects with phonophobia absent at the time point for the subset with phonophobia present at the time of dosing
Summary	Percentage of subjects with phonophobia freedom over time by treatment group for the efficacy analysis set
Intercurrent Events	Rescue medication use at or before time point: Composite strategy, i.e., intercurrent event captured in endpoint definition
Objective	Photophobia freedom at all time points postdose
Efficacy Endpoint	At each time point postdose, percentage of subjects with photophobia absent at the time point for the subset with photophobia present at the time of dosing
Summary	Percentage of subjects with photophobia freedom over time by treatment group for the efficacy analysis set
Intercurrent Events	Rescue medication use at or before time point: Composite strategy, i.e., intercurrent event captured in endpoint definition
Objective	Nausea freedom at all time points postdose
Efficacy Endpoint	At each time point postdose, percentage of subjects with nausea absent at the time point for the subset with nausea present at the time of dosing
Summary	Percentage of subjects with nausea freedom over time by treatment group for the efficacy analysis set
Intercurrent Events	Rescue medication use at or before time point: Composite strategy, i.e., intercurrent event captured in endpoint definition
Objective	MQoL
Outcomes Research Endpoint	Change from baseline in the total score at end of treatment visit
Summary	Mean change from baseline in total score by treatment group for the efficacy analysis set
Intercurrent Events	Rescue medication use: Treatment policy strategy, i.e., no accounting for intercurrent event
Objective	PoM
Outcomes Research Endpoint	Percentage of subjects who prefer study medication to previous migraine medications
Summary	Percentage of subjects in each category by treatment group for the efficacy analysis set with PoM data
Intercurrent Events	Rescue medication use: Treatment policy strategy, i.e., no accounting for intercurrent event
Objective	Safety and tolerability

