Analyses are based on non-missing, postdose efficacy data relevant to each endpoint.

For a given time-to-event endpoint, subjects are considered to have an event through X hours ($X = 4$ or 8) if the first postdose eDiary finding date/time defining response is (1) at or before the upper bound of the X -hour analysis window in minutes (see Table 5), and (2) is before the imputed rescue medication start date/time, if not missing (see Section 7.1).

Otherwise, subjects who do not have an event through X hours are censored at the earliest of the following: (1) upper bound of the X -hour analysis window + 1 minute; (2) time from the study drug start date/time to the imputed rescue medication start date/time, if the time is at or before the upper bound of the X -hour analysis window in minutes; (3) time from the study drug start date/time to the last non-missing finding date/time defining the endpoint, if the time was before the lower bound of X -hour analysis window in minutes.

For each endpoint listed above, time to event is assessed by treatment group as follows:

- Kaplan-Meier plot and table using the following time intervals postdose: 0 to 15, >15 to 30, > 30 to 45, > 45 to 60, > 60 to 90, > 90 to 120, > 120 to 180, > 180 to 240, > 240 to 360, > 360 to 495, and > 495 minutes. The Kaplan-Meier plot displays the percentage of subjects with the event on the y-axis versus time in minutes on the x-axis.
- Time-to-event distribution table (minutes), including a log-rank p-value (zavegepant versus placebo).

See Section 6.1.1.1 for additional table and plot attributes.

6.3.4.4 *Efficacy Endpoints Compared over Time*

Treatment group comparisons of the percentage of subjects achieving response over time use analogous methods as the main analysis of the co-primary endpoint of pain freedom with NC=F and RM=F (see Section 6.3.2.1) for the efficacy analysis set and the following endpoints:

- Pain freedom
- Pain relief
- MBS freedom
- Return to normal function for subjects with functional disability at the time of dosing
- Phonophobia freedom for subjects with phonophobia present at the time of dosing
- Photophobia freedom for subjects with photophobia present at the time of dosing

- Nausea freedom for subjects with nausea present at the time of dosing.

For each endpoint and time point from 15 minutes through 48 hours postdose, the following are presented:

- Response rate (i.e., “n/N” and percentage), ASE, and 95% CI for each treatment group

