6.5.2 PoM

The PoM is a 5-point rating scale that measures the patient's preference of study medication to previous medications to treat migraine pain from much better to much worse. Refer to the Zavegepant Core SAP for the 5 categories and additional combined categories.

PoM are tabulated as the number and percentage of subjects in each preference category (including combined categories) by as-randomized treatment group. Percentages are presented with exact Clopper-Pearson 95%. Analyses are provided for the following: (1) overall; (2) by pain freedom outcome at 2 hours postdose (responder, failure) for subjects who are included in the complete cases sensitivity analysis of pain freedom at 2 hours postdose (see Section 6.3.2.1).

A by-subject listing of PoM is provided for the enrolled analysis set.

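### MQoL and PoM are summarised by arm only: exploratory objectives 8 and 9 get a description, but no planned between-arm contrast with its uncertainty

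*SAP*

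**What the plan says.** **Objectives (SAP 3.1.3; same in Protocol 2.3).** Objective 8: "To evaluate zavegepant relative to placebo for the Migraine Quality of Life Questionnaire (MQoL"). Objective 9: "To evaluate zavegepant relative to placebo for the Preference of Medication (PoM"). Objectives 1 to 7 open with the same words. The secondary objectives use a different verb, for example "To compare zavegepant with placebo for pain relief at 2 hours postdose".

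**Planned outputs.** For MQoL, SAP 6.5.1: "MQoL total, domain, and item scores are tabulated by as-randomized treatment group", as continuous variables and as categories. For PoM, SAP 6.5.2: "PoM are tabulated as the number and percentage of subjects in each preference category", by arm, with exact Clopper-Pearson intervals on the percentages, overall and split by 2-hour pain freedom outcome. SAP 6.5 bases both on observed data, without imputation and regardless of rescue medication.

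**Other exploratory endpoints.** SAP 6.3.4.4: "Treatment group comparisons of the percentage of subjects achieving response over time use analogous methods" as the co-primary analysis. It gives a stratified difference with ASE, 95% CI and p-value for seven endpoints, those of objectives 1 to 7. MQoL and PoM are not among them.

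**Estimands (SAP Table 3).** The MQoL endpoint is "Change from baseline in the total score at end of treatment visit", summarised as "Mean change from baseline in total score by treatment group for the efficacy analysis set". PoM is also summarised by arm.

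**The concern.** An objective phrased relative to placebo calls for an estimate of the difference between arms and a statement of how precise it is. Here the randomised 24-hour data exist in both arms and the SAP already has a suitable method, yet the two patient-reported scales are left as parallel columns. Any contrast in the study report would have to be built afterwards, and someone would then choose the PoM category or MQoL domain after seeing the results. Settling that choice before unblinding costs almost nothing.

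The MQoL entry in Table 3 adds a second problem. A contrast cannot be specified properly while the stated endpoint differs from what is collected.

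**Working it through.** **1. The plan's own figure.** The documents give no precision or power figure for MQoL or PoM. The only design calculation is in SAP 5, and it supplies the sample size used below: 700 × 0.90 = 630 per arm. With a two-sided alpha of 0.05 and pooled variance under the null,

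power = Φ{ [ |p1 − p2| − 1.96·√(2p̄(1 − p̄)/n) ] / √(p1(1 − p1)/n + p2(1 − p2)/n) }

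- Pain freedom, 22.8% v 15.5%: (0.073 − 0.0435)/0.0221 = 1.34, power 90.96% (stated 91%).
- MBS freedom, 42.2% v 33.7%: (0.085 − 0.0536)/0.0272 = 1.15, power 87.56% (stated 88%).
- Joint, as a product: 79.65% (stated 80%).

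The figures reproduce, so 630 is a fair working number.

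**2. Planned output against objective.**

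| Exploratory objective | Objective wording | Table 3 summary | Between-arm difference planned |
|---|---|---|---|
| 1–7 (pain, MBS, function, symptoms) | evaluate relative to placebo | by arm | yes, SAP 6.3.4.4, with 95% CI and p-value |
| 8 (MQoL) | same | by arm | none in SAP 6.5.1 |
| 9 (PoM) | same | by arm | none in SAP 6.5.2 |

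**3. MQoL endpoint against collection.** Protocol Table 1, 4.3.2.1 and 6.5.1 and SAP 7.5.3 place MQoL at 24 hours postdose only; the SAP window is 23 to 29 hours. No baseline MQoL is scheduled and none is scheduled at the end of treatment visit. SAP 6.5.1 plans no change score. The change from baseline named in Table 3 therefore cannot be computed from the scheduled data.

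**4. What a contrast would deliver.** The documents give no PoM rates and no MQoL SD, so these inputs are assumptions. The 95% half-width of a PoM difference is 1.96·√(2p(1 − p)/n), and of an MQoL mean difference in SD units 1.96·√(2/n).

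| n per arm | PoM rate 20% | 30% | 50% | MQoL |
|---|---|---|---|---|
| 630 | ±4.4 points | ±5.1 | ±5.5 | ±0.11 SD |
| 504 (assumed 20% missing) | ±4.9 | ±5.7 | ±6.2 | ±0.12 SD |

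**5. What the by-arm PoM table already allows.** Suppose 284/630 v 324/630 (45.1% v 51.4%, illustrative). The difference is 6.3 points. SE = √(0.2476/630 + 0.2498/630) = 0.0281, so the 95% CI is 0.8 to 11.9. The exact arm intervals (41.1 to 49.1 and 47.4 to 55.4) overlap. The contrast can thus be recovered without stratification from the counts, but the plan does not provide it.

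**The case against.** The best defence is that the SAP does what it says. Table 3 prespecifies by-arm summaries for both objectives, and for PoM SAP 6.5.2 delivers exactly that form. The exploratory objectives say evaluate where the secondary ones say compare. Objective 11 (S-STS) has the same wording and is also summarised by arm only. Limiting unadjusted comparisons on exploratory endpoints is a defensible choice.

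Much of this stands. The wording alone does not promise an inferential contrast. It does not explain the uneven treatment, however: objectives 1 to 7 share both the verb and the by-arm summaries in Table 3, yet received contrasts through SAP 6.3.4.4, a section that the revision history lists as new in SAP Version 5.0.

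Two stronger readings are tempting and are not supported:

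- *A reader might infer that objectives 8 and 9 go unanswered.* They do not. Both randomised arms are tabulated side by side, so the objectives are addressed descriptively.
- *A reader might infer that arms can be compared only by seeing whether their intervals overlap.* The SAP states no such rule. The PoM counts yield an unstratified difference and CI, as step 5 shows. SAP 6.5.1 names no within-arm interval for MQoL.

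The Zavegepant Core SAP is not available. The SAP cites it for scoring, categories, descriptive statistics and scale details, not for a treatment comparison. A contrast there cannot be ruled out, but if one exists SAP 6.5 should point to it.

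**Conclusion.** The concern holds as a modest gap. In the documents available, no between-arm contrast with its uncertainty is planned for MQoL or PoM, while the identically worded objectives 1 to 7 have one. The consequence is small: there is no effect on power, type I error, or the primary and secondary conclusions, and SAP 5 treats any exploratory p-value as descriptive. The likely precision of a PoM difference, about ±5 to ±5.5 points, rests on an assumed 630 per arm and assumed rates of about 30% to 50%; missing 24-hour data would widen it.

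The mismatch between Table 3 and the MQoL collection schedule depends on no assumption. It should be resolved before any MQoL contrast is written.

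**What to change.** - **SAP 6.5.2 (PoM):** prespecify one combined category in which study drug is rated better than previous medication, consistent with the Core SAP's combined categories. Add the stratified difference (zavegepant − placebo) with 95% CI by the SAP 6.3.2.1 method. Apply it to observed data, without the failure rules for missing data or rescue use, in keeping with SAP 6.5. Confine it to the overall tabulation, because the split by 2-hour response is defined after randomisation.
- **SAP Table 3 (MQoL):** restate the endpoint and summary as the 24-hour postdose score actually collected.
- **SAP 6.5.1 (MQoL):** add the difference in mean 24-hour total and domain scores with 95% CI, stratified by IWRS prophylactic medication use.
- **Labelling:** mark both as descriptive and unadjusted, as SAP 5 already provides for exploratory endpoints.

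If the sponsor prefers no contrast, the alternative is to reword objectives 8 and 9 as by-arm description; the Table 3 correction is still needed.

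The cost is a few columns in existing tables, with no new data. The downside is 1 PoM + 1 MQoL total + 5 MQoL domains = 7 further unadjusted comparisons.
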